<70	
Discontinue exenatide infusion.
 
Give 25 mL of dextrose 50% (1/2 amp) IVP – Recheck glucose in 5 minutes and notify physician.
 
Check glucose hourly after hypoglycemia is resolved.
 
When 2 in a row hourly glucose checks are greater than 109 restart exenatide infusion at 25 ng/min
 
Notify physician when glucose greater than 80 mg/dL
 
Monitor blood pressure continuously during infusion (if SBP <100 mmHg, contact physician)

80-109	
Temporarily discontinue exenatide infusion
 
Check glucose hourly
 
When glucose greater than 109 restart exenatide infusion at 25 ng/min
 
Note: If 3 in a row hourly checks are less than 110 restart protocol from beginning. Change glucose check to q4h and exenatide protocol for second glucose greater than 180 mg/dL
 
Monitor blood pressure continuously during infusion (if SBP <100 mmHg, contact physician)

110-180	Continue exenatide infusion per protocol Check glucose hourly Monitor blood pressure continuously during infusion (if SBP<100 mmHg, contact physician)
181-216	1 st hourly glucose check (=1 hour since exenatide initiation): continue exenatide infusion protocol ≥2 nd hourly glucose check (≥2 hours since exenatide initiation): Give 2 units of formulary available rapid acting insulin subcutaneously and continue exenatide infusion protocol Check glucose hourly Monitor blood pressure continuously during infusion (if SBP <100 mmHg, contact physician)
217-252	1 st hourly glucose check (=1 hour since exenatide initiation): continue exenatide infusion protocol ≥2 nd hourly glucose check (≥2 hours since exenatide initiation): Give 4 units of formulary available rapid acting insulin subcutaneously and continue exenatide infusion protocol Check glucose hourly Monitor blood pressure continuously during infusion (if SBP <100 mmHg, contact physician)
253-300	1 st hourly glucose check (=1 hour since exenatide initiation): continue exenatide infusion protocol ≥2 nd hourly glucose check (≥2 hours since exenatide initiation): Give 6 units of formulary available rapid acting insulin subcutaneously and continue exenatide infusion protocol Check glucose hourly Monitor blood pressure continuously during infusion (if SBP <100 mmHg, contact physician)
>300	Recheck blood glucose within 5 minutes If confirmed, contact physician to discontinue exenatide and initiate rescue insulin infusion protocol (NSICU insulin infusion protocol)

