3. Glycemic Variability Protocol: The Guardian REAL-Time Continuous Glucose Monitoring System (CGMS, Medtronic MiniMed, Northridge, CA) will be used to assess glycemic variability. The CGMS device carries an FDA-approved indication to supplement but not replace routine standard monitoring in patients. As such, the nursing staff will be blinded to the CGMS readings. All therapeutic decisions will be based upon standard of care glucose monitoring as outlined in the glycemic control protocol.

The CGMS is composed of a subcutaneous sensor that uses the glucose oxidase reaction for generation of an electrical current. A wireless transmitter connects to the sensor, and the signal is analyzed and converted to a measurement of the subcutaneous glucose level by a pager-sized device. Glucose levels are measured and recorded every 5 minutes. The subcutaneous glucose sensor will be deployed using the insertion kit available by the manufacturer. The sensors will be preferentially placed in the anterior abdomen. In the event the anterior abdomen is not available, the sensor will be placed in the upper thigh. Routine blood glucose measurements will be obtained hourly while the patient is receiving exenatide for purposes of calibration of the CGMS. After the initial calibration, the CGMS will be calibrated every 12 hours at a minimum. Sensors will be monitored daily by an investigator and 1 day after removal. The CGMS will be performed for 72 hours (48 hours during study drug infusion and an additional 24 hours during follow-up after study drug is discontinued).

4. Pharmacokinetic Protocol:

All patients admitted to the NSICU that meet the eligibility criteria will be approached for consent of blood samples obtained for pharmacokinetic analysis. Blood samples will be collected at 0, 12, 24, 36, and 48 hours after the start of the infusion. Approximately 30 mL of blood will be collected over 48 hours for pharmacokinetic sampling. The exenatide concentrations will be processed by Tandem Labs. An 8-hour urine collection for measuring creatinine clearance will be performed as the primary method of measuring renal

function. Eight-hour urine collections will be obtained on a daily basis for 72 hours (48 hours during study drug infusion and an additional 24 hours during follow-up after study drug is discontinued).

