2 DATA MONITORING COMMITTEE AND OTHER EXTERNAL COMMITTEES

Not applicable

8. Measurements: Blood glucose from the arterial line will be measured at baseline (prior to exenatide), hourly during the 48 hour exenatide infusion per protocol (table 2) and continue for an additional 24 hours following exenatide discontinuation. The continuous glucose monitor will measure the interstitial glucose level every 5 minutes beginning at baseline (prior to exenatide) until 24 hours following exenatide discontinuation. Blood samples for pharmacokinetic analysis will be collected in serum separator tubes at 0, 12, 24, 36 and 48 hours after the start of the infusion. Eight-hour urine collections will be obtained on a daily basis for 72 hours (48 hours during study drug infusion and an additional 24 hours during follow-up after study drug is discontinued). Microdialystate concentrations will be collected at baseline (prior to exenatide), and hourly during the 48-hour exenatide infusion for parameters of energy metabolism (glucose, pyruvate, lactate, lactate:pyruvate ratio), glutamate (marker of cerebral ischemia), and glycerol (marker of cell membrane degradation) and for an additional 24 hours following study drug discontinuation. Blood pressure will be measured continuously throughout the study period. Intracranial pressure (ICP) will be measured continuously during the exenatide infusion. Intracranial pressure values will be recorded at baseline (prior to exenatide) and daily mean ICP and cerebral perfusion pressure values will be reported. Baseline demographic information (e.g. gender, age, ethnicity) and disease severity information [e.g. Glasgow coma score, SOFA score (Sequential Organ Failure Assessment), Hunt Hess classification, Fisher grade, primary diagnosis, past medical history (including measurement of hemoglobin A1c), neurologic exam/computed tomography scan abnormalities] will be collected. The ICU day of study drug administration will be recorded and the total hospital and ICU lengths of stay will be recorded.

9. Data Management: Each participant will be assigned a unique identification number. No personal identification will be used. All study files will be stored in locked cabinets in the Principal Investigator's office in the Pharmacy Administration Department. Data will be entered into the study database using double entry (entry and verification) and will be checked for missing or ineligible responses.

10. Outcomes

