10.1 The following feasibility endpoints are based upon prior literature (Nice-Sugar and Exenatide Study in the Cardiac ICU):

Proportion of patients experiencing severe hypoglycemia (<40 mg/dL), Proportion of patients achieving plasma glucose goal (110-180 mg/dL), Proportion of patients experiencing nausea requiring discontinuation of exenatide therapy

10.2 The following descriptive endpoints are included for describing experience with exenatide use in the NSICU population:

Average blood glucose value during exenatide infusion (48 hours), percent time in glucose range (48 hours), mean time to reach plasma glucose goal (110-180 mg/dL), variability outcome (SD)-MADGE, mean insulin use required (units/kg body weight), proportion of subjects requiring rescue insulin infusion protocol, number of hypoglycemic episodes (<80 mg/dL)/total number of glucose measurements (48 hours), number of subjects with >1 hypoglycemic episode (<80 mg/dL)/total number of subjects (48 hours), correlation of exenatide concentrations with creatinine clearance during infusion, elimination rate constant and area under the concentration-time curve utilizing concentrations after discontinuation of infusion, side effects and adverse events (AEs and SAEs), average daily ICP and CPP during study drug infusion, number of hypotensive episodes (SBP<100 mmHg) (48 hours), number of subjects with >1 hypotensive episode/total number of subjects (48 hours). Other adverse effects will be collected specifically assessing any alterations in gastric motility.

In patients receiving invasive intracranial multimodal monitoring as part of their standard of care, the following endpoints associated with exenatide use will be described:

Percent time outside of range for energy metabolism (glucose <0.7 mmol/L and lactate:pyruvate ratio > 40), glutamate (marker of cerebral ischemia), and glycerol (marker of cell membrane degradation) parameters (48 hours).

Based upon prior literature, the prespecified criteria for determining feasibility include the following: 1) no more than 6 patients (25%) experiencing severe hypoglycemia (<40 mg/dL); 2) at least 18 patients (75%) achieving the plasma glucose goal (110-180 mg/dL); 3) no more than 6 patients (25%) experiencing nausea leading to exenatide discontinuation. These criteria will be utilized to determine whether a future efficacy trial will be pursued.

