11. Sample size and justification: A sample size was determined using prior exenatide in critically ill patients studies and patient screening information at our site. Based upon this data, we determined to enroll 24 patients who complete 48 hours of exenatide infusion and continuous glucose monitoring. In eligible patients, cerebral microdialysis monitoring will also be performed. It is estimated based on proposed eligibility criteria that 24% (n = 200) patients admitted to the NSICU will be eligible for enrollment annually. With an approximate rate of enrollment at 15 – 20%, we are confident we could enroll 30 – 40 subjects annually.

12. Data analysis plan: Prior to analysis, data will be examined for errors, outliers, and asymmetry. When appropriate, transformations will be used to reduce asymmetry. An intent-to-treat analysis (defined as all individuals consented in the study) will be utilized. Descriptive statistics will be performed. Data will be expressed as means \pm standard error (SE) or success rates and corresponding 95%CI for continuous and

dichotomous outcomes, respectively. Analyses will be completed using the statistical software package SAS, version 9.2 (SAS institute, Cary, North Carolina).

13. Ethical consideration: The consent procedures will be reviewed and approved by the Institutional Review Board. All subjects will provide written informed consent via proxy. The informed consent process will allow the proxy to gain an in-depth knowledge of the study purposes and procedures and allow them to make informed decisions about willingness to proceed. Participation is voluntary. The proxy will be encouraged to ask questions and will be assessed for adequate understanding.

Exenatide required: yes

Placebo required: no

Clinical study duration of treatment: Subjects will be exposed to exenatide treatment for 48 hours.

Clinical study dosing schedule and frequency: exenatide 50 ng/min for 30 minutes, start exenatide infusion 25 ng/min x 48 hours

Clinical study number of sites: one

Clinical study expected number of subjects screened: It is estimated based on proposed eligibility criteria that 24% (n = 200) patients admitted to the NSICU will be eligible for enrollment annually with an approximate rate of enrollment at 15-20%.

Clinical study expected number of subjects enrolled: 24

Clinical study expected number of subjects to complete study: 24

Planned Study Start Date: January 1, 2015

Planned Study End Date: June 30, 2016

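### The hypoglycemia ratio pools repeated glucose readings from 24 patients, and a binomial 95% CI computed on those readings would be too narrow

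*Combined protocol and SAP*

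**What the plan says.** Section 10.2 includes among its descriptive endpoints "number of hypoglycemic episodes (<80 mg/dL)/total number of glucose measurements (48 hours". The next endpoint counts subjects with more than one such episode over the total number of subjects, so the plan itself separates readings from patients as units.

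The glucose source for the ratio is not named. Section 8 (Measurements) has arterial-line glucose taken "hourly during the 48 hour exenatide infusion per protocol (table 2"), and also states: "The continuous glucose monitor will measure the interstitial glucose level every 5 minutes". Table 2 adds unscheduled readings after a value below 70 mg/dL: "Recheck glucose in 5 minutes and notify physician".

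Section 11 sets the number of patients: "we determined to enroll 24 patients who complete 48 hours of exenatide infusion and continuous glucose monitoring". Section 12 plans descriptive statistics, means with standard errors for continuous outcomes, and "success rates and corresponding 95%CI" for dichotomous ones. It names no interval method and no adjustment for repeated measurements. By contrast, section 5 specifies a summary per patient for the hourly microdialysis data.

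Section 10.2 also lists "correlation of exenatide concentrations with creatinine clearance during infusion". Section 4 schedules the exenatide samples: "Blood samples will be collected at 0, 12, 24, 36, and 48 hours after the start of the infusion". It schedules one eight-hour urine collection per day.

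**The concern.** A glucose value is either below 80 mg/dL or not, so the ratio resembles a success rate, and an analyst following section 12 could reasonably attach a binomial interval to the pooled count. That interval treats every reading as a separate piece of information. In practice, one low spell can yield several consecutive low values, and some patients are more prone to low glucose than others. The independent units are the 24 patients.

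Hypoglycemia matters in this study. The rationale for Aim 1 says it should be strictly avoided, and the rationale for Aim 3 cites an observational study linking a nadir below 80 mg/dL to infarction, vasospasm and poor functional outcome. A falsely tight interval could mislead the designers of a later trial about how well the rate is known.

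There is also a mismatch of units. The numerator counts episodes, which are not defined, while the denominator counts measurements. Low values themselves change the number of measurements, through the five-minute rechecks and through the move in Table 2 to four-hourly checks after three consecutive readings below 110 mg/dL.

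**Working it through.** **The plan's own figures.** The documents give no interval, standard error or ICC for this ratio. The sample size of 24 has no formula behind it and cannot be re-derived. The feasibility thresholds check arithmetically: 6/24 = 25% and 18/24 = 75%.

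**Inputs.**
- Patients: 24 (section 11).
- Readings per patient: 48 if hourly arterial values are used (section 8), leaving out the baseline value and rechecks. Total 24 × 48 = 1,152. Four-hourly checking in some patients would lower this.
- Readings per patient if the continuous monitor is used: 12 per hour × 48 = 576. Total 24 × 576 = 13,824.
- ICC and true rate: assumptions, shown as ranges.

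**Width.** With m readings per patient, the variance of the pooled proportion is multiplied by the design effect 1 + (m − 1) × ICC, and the interval width by its square root. At an assumed 5% rate the half-width under independence is 1.96 × √(0.05 × 0.95 / 1,152) = 1.26 percentage points. For hourly readings (m = 48):

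| Assumed ICC | Design effect | Width factor | Effective readings | Half-width at 5% rate (points) |
|---|---|---|---|---|
| 0.01 | 1 + 47 × 0.01 = 1.47 | 1.21 | 784 | 1.53 |
| 0.02 | 1 + 47 × 0.02 = 1.94 | 1.39 | 594 | 1.75 |
| 0.05 | 1 + 47 × 0.05 = 3.35 | 1.83 | 344 | 2.30 |
| 0.10 | 1 + 47 × 0.10 = 5.70 | 2.39 | 202 | 3.00 |

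With the continuous monitor (m = 576), the width factor is √(1 + 575 × 0.01) = 2.60 at an ICC of 0.01 and √(1 + 575 × 0.10) = 7.65 at 0.10.

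**Coverage.** Beta-binomial simulation with 24 patients, 48 readings each, 20,000 runs and true rates of 2% to 10%. A nominal 95% exact interval on the pooled count covers the true rate about 90-92% of the time at an ICC of 0.01, 85-88% at 0.02, 73-76% at 0.05 and 60-62% at 0.10.

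**Does a simple patient-level interval repair this?** Mostly, but not when events are rare. A t interval on the 24 patient shares covers 94% at a 5% rate and ICC 0.02, and 91% at ICC 0.10. At a 2% rate it covers 92% and 84%.

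**The correlation.** Of the five exenatide samples, four follow the start of infusion. Of the three daily clearance values, two fall within the 48 hours. With k pairs per patient, the width factor for an interval that ignores patients is about √(1 + (k − 1) × ICC₁ × ICC₂), where the two ICCs belong to concentration and clearance. For k = 2 it cannot exceed √2 = 1.41. With both ICCs at 0.5 to 0.9 it is 1.12 to 1.35.

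**The case against.** The strongest reply is that the plan never says readings will be treated as independent. Section 12 is silent on the matter, and it also promises plain descriptive statistics, so a ratio with no interval would comply. So would a share computed per patient and reported as mean with standard error, which is close to the remedy. This stands: the point concerns what happens if the one interval format in section 12 is applied to the pooled count. It is not a documented error.

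Two further replies stand in part. The simulation counts readings below 80 mg/dL, whereas the endpoint counts episodes. If an episode spanning several readings counts once, clustering would be weaker, but the documents do not define an episode. The size also depends on an ICC that nobody has stated: at 0.01 to 0.02 with hourly readings the loss is modest.

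A reader might infer that the same fault undermines the correlation in Aim 2, with up to 24 × 4 = 96 pairs standing in for 24 patients. The documents do not support that. They plan no interval, test or significance level for the correlation. Reaching 96 pairs would mean using each clearance value twice, which is not stated. With two pairs per patient, a 5% test that ignored patients would reject about 8-15% of the time under no association (both ICCs 0.5 to 0.9), but the plan contains no such test. Setting 96 pairs against 24 patients also assumes perfect within-patient correlation.

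Finally, section 10.2 is descriptive, and a per-patient hypoglycemia proportion is reported alongside.

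**Conclusion.** The concern holds conditionally. A binomial 95% CI on the pooled hourly readings would be too narrow by a factor of about 1.2 to 1.4 at an ICC of 0.01 to 0.02, 1.8 at 0.05 and 2.4 at 0.10. If continuous-monitor readings are the source, the factor is larger at the same ICC. These figures assume 24 patients with equal numbers of readings and an ICC outside the documents.

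A reader might infer that the study's conclusion is at risk. It is not: all three feasibility criteria count patients, and neither the ratio nor the correlation enters them. What is at stake is the stated precision of one safety description. It is worth correcting because the remedy is so cheap. The correlation is a matter of missing detail only.

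**What to change.** In section 12:

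1. Name the glucose source for the ratio (arterial line or continuous monitor).
2. Use one unit throughout: scheduled readings below 80 mg/dL over scheduled readings, leaving out the five-minute rechecks. State how periods of four-hourly checking are treated. If episodes are also reported, define one and give them as a count per patient.
3. Compute the share for each patient and summarize across patients, with an interval clustered on patient (for example a patient-level bootstrap, or GEE with robust variance). Specify a small-sample correction, because there are only 24 clusters and low values may be rare.
4. As a secondary clarification, if any interval or p-value is given for the exenatide-clearance correlation, use one mean concentration and one mean on-infusion clearance per patient, or a repeated-measures method.

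The cost is a few lines of code on data already being collected. The drawback is a wider, less favorable interval.

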for the second consecutive blood glucose value >150 mg/dL but ≤ 300 mg/dL and continue per protocol for a maximum duration of 48 hours. Exenatide will be administered by intravenous infusion (50 ng/min for 30 minutes, then start exenatide infusion 25 ng/min) for the second consecutive blood glucose value >150 mg/dL but ≤ 300 mg/dL and continue per protocol for a maximum duration of 48 hours (dose, route, titration schedule, and duration). Exenatide will be prepared by the Investigational Drug Service. The exenatide infusion initiation and maintenance protocols are outlined in Tables 1&2 of the attached study protocol. The exenatide infusion blood glucose goal will be 110-180 mg/dL. During the exenatide infusion, glucose measurements will be obtained hourly. The exenatide infusion will be temporarily discontinued for blood glucose <110 mg/dL. The exenatide infusion will be restarted once the blood glucose level is at least 110 mg/dL. Episodes of hypoglycemia will be treated according to the following guidelines: 1) glucose <70 mg/dL will be provided 25 mL of dextrose 50% (1/2 amp) 2) blood glucose will be re-checked in 5 minutes; if mental status changes caused by hypoglycemia are not reversed or blood glucose remains <70 mg/dL, the above dextrose administration will be repeated, 3) serum glucose will be checked hourly after dextrose administration and the episode has resolved. Exenatide infusion will be restarted beginning with the second hourly glucose check that is ≥ 110 mg/dL. Insulin sensitive sliding scale using formulary rapid acting insulin will be used for blood glucose 181-300 mg/dL starting at the 2nd hourly glucose check (≥ 2 hours since exenatide initiation). The physician will be notified for any blood glucose >300 mg/dL for initiation of a rescue insulin infusion protocol. All glucose values will be documented in the ICU Electronic Documentation System.

Table 1: Exenatide Infusion Initiation Protocol

Glucose (mg/dL)	Action
151-300	
Give exenatide 50 ng/min for 30 minutes, then start exenatide infusion 25 ng/min
 
Give prokinetic agent per NSICU protocol (reglan, erythromycin, etc)
 
Check glucose hourly
 
Monitor blood pressure continuously during exenatide infusion. If SBP <100 mmHg, contact physician. Decision to discontinue exenatide infusion will be made at the discretion of the treating physician.

Table 2: Exenatide Infusion Maintenance Protocol

Glucose (mg/dL)	Action

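### The frequency of hypoglycemia below 80 mg/dL is divided by a count of glucose readings that Table 2 changes with the glucose level

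*Combined protocol and SAP*

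**What the plan says.** Among the descriptive endpoints in item 10.2 (Outcomes) is "number of hypoglycemic episodes (<80 mg/dL)/total number of glucose measurements (48 hours"). The next endpoint in that list counts subjects with more than one such episode, divided by all subjects. The item does not define an episode. It also does not say whether the measurements are blood readings or continuous glucose monitor (CGM) readings, or whether the 48 hours are clock time or infusion-on time.

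The default schedule in item 2 (Glycemic Control Protocol) is hourly: "During the exenatide infusion, glucose measurements will be obtained hourly". Item 8 (Measurements) adds a baseline reading and sets blood glucose checks "hourly during the 48 hour exenatide infusion per protocol (table 2"), so Table 2 governs. The infusion is to "continue per protocol for a maximum duration of 48 hours".

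Table 2 then changes the frequency in two ways:

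- In the 80-109 mg/dL row: "If 3 in a row hourly checks are less than 110 restart protocol from beginning", followed by "Change glucose check to q4h and exenatide protocol for second glucose greater than 180 mg/dL".
- In the row below 70 mg/dL: "Recheck glucose in 5 minutes and notify physician".

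**The concern.** The denominator depends on the variable being summarised. A patient whose glucose stays below 110 mg/dL for three checks is read less often. A patient who falls below 70 mg/dL is read more often for a short time. Two patients with the same number of episodes in the same 48 hours can therefore have different ratios, and nothing in the plan fixes, weights or standardises the count.

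The background section makes strict avoidance of hypoglycemia part of the rationale and cites an association between a nadir below 80 mg/dL and poor outcome. The study has no control arm, so a reader will compare its figure with outside experience. That needs a recognisable unit, such as episodes per patient-day or percent of time. The companion endpoint does not fill the gap: it counts only subjects with more than one episode, so it captures neither a single episode nor its duration.

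**Working it through.** The plan states no expected rate or number of readings, so there is no figure to reproduce. The check counts readings directly.

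**Inputs.** Hourly checks (items 2 and 8); 48-hour window (item 10.2); 4-hourly checks after three consecutive hourly values below 110 mg/dL, until a second value above 180 mg/dL (Table 2); at least one extra reading 5 minutes after a value below 70 mg/dL (Table 2); 24 patients (item 11). Assumptions: arterial readings, 48 clock hours, and the same number of detected episodes under both schedules.

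**1. One patient, switched at hour s and not returned to hourly checks.** Readings = s + floor((48 − s)/4), against 48 if hourly throughout. Counting the baseline reading adds 1 to each. Fold difference = 48/readings, or 49/readings with baseline.

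| Switch hour s | Readings | One episode | Fold vs 1/48 = 2.08% | Fold with baseline |
|---|---|---|---|---|
| 3 (earliest) | 3 + 11 = 14 | 7.14% | 3.43 | 49/15 = 3.27 |
| 6 | 6 + 10 = 16 | 6.25% | 3.00 | 49/17 = 2.88 |
| 12 | 12 + 9 = 21 | 4.76% | 2.29 | 49/22 = 2.23 |
| 24 | 24 + 6 = 30 | 3.33% | 1.60 | 49/31 = 1.58 |
| 36 | 36 + 3 = 39 | 2.56% | 1.23 | 49/40 = 1.23 |

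**2. Return to hourly checks.** With a switch at hour 3 and hourly checks again after hour 11, 19 or 27, the readings with baseline are 43, 37 and 31. The fold differences are 49/43 = 1.14, 49/37 = 1.32 and 49/31 = 1.58.

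**3. Five-minute rechecks alone.** One to six extra readings change the denominator by 50/49 = 1.02 to 55/49 = 1.12. This lowers the ratio.

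**4. Pooled over 24 patients.** Hourly throughout gives 24 × 48 = 1152 readings. If x patients switch at hour 12 and stay there, the denominator is (24 − x) × 48 + x × 21:

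- x = 4: 1152/1044 = 1.10
- x = 6: 1152/990 = 1.16
- x = 12: 1152/828 = 1.39

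If the switch comes at hour 3 (baseline counted, 24 × 49 = 1176), 3, 6 or 12 patients give 1176/1074 = 1.09, 1176/972 = 1.21 and 1176/768 = 1.53. The documents give no basis for the number who switch, so these are a range and not a forecast.

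**5. Patient-time denominator.** One episode in 48 hours is 1/(48/24) = 0.5 per patient-day under either schedule, a fold difference of 1.0. This removes the denominator effect only.

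**The case against.** The strongest case on the other side has five parts.

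- **The calculation holds the numerator fixed.** Four-hourly checks also detect fewer lows, which offsets the smaller denominator. This stands. The documents do not allow the offset to be sized, so the pooled inflation is best read as an upper figure for the assumed number of switches.
- **Three-fold is an extreme.** It needs a switch by about hour 6 and no return to hourly checks. The trigger is three values below 110 mg/dL, not hypoglycemia itself, and the endpoint's wording reads naturally as a cohort total. This stands too. A reader might infer that the reported rate will be wrong by a factor of three; the documents do not support that.
- **The effect depends on unstated readings of the endpoint.** If 48 hours means infusion-on time, the 4-hourly period largely drops out, because the infusion is off then. If CGM values count, the denominator is a fixed 48 × 12 = 576 and the artefact disappears, but the ratio is then about 12 times smaller than with arterial readings (576/49 = 11.8). These gaps are themselves a reason to rewrite the definition.
- **Other summaries exist.** Item 10.2 has the per-subject count at the same threshold, percent time in range, severe hypoglycemia below 40 mg/dL, and adverse events. It would therefore be wrong to call this ratio the only information on hypoglycemia. None of these, however, gives the frequency of single episodes below 80 mg/dL or their duration.
- **An episode is undefined.** A reader might infer that a prolonged low is scored as one mild event, or that the ratio understates the share of low readings. Both need a rule that merges consecutive lows, which the plan does not state. If every reading below 80 mg/dL is an episode, the ratio is simply the proportion of low readings and that criticism falls. The dependence on sampling remains. An example of a six-hour low checked hourly throughout would also sit badly with the rule that moves checks to every 4 hours after three values below 110 mg/dL.

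**Conclusion.** The point holds as a minor one. As written, the ratio changes with how often glucose is checked, and Table 2 ties that to the glucose level. On arterial readings over 48 clock hours, the same detected count gives a ratio about 1.6 times higher for a switch at hour 24 and about 3 times higher at the single-patient extreme. Pooled over 24 patients the figure is about 10% to 40% if 4 to 12 switch at hour 12. Those numbers of patients are assumed, and missed episodes offset part of the effect. Rechecks pull slightly the other way.

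A reader might also infer that the feasibility decision is at risk. It is not: the three criteria concern severe hypoglycemia below 40 mg/dL, reaching the glucose goal, and nausea leading to discontinuation, and none uses this denominator. No test or group comparison depends on it either.

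**What to change.** In item 10.2, replace the ratio with episodes below 80 mg/dL per 24 hours of monitored time in the 48-hour window. State three things with it: arterial blood glucose is the source; consecutive values below 80 mg/dL count as one episode until a value of 80 mg/dL or more; and whether the window is clock time from the start of infusion or infusion-on time.

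Report percent of monitored time below 80 mg/dL alongside, with each reading weighted by the interval it represents, so that a 5-minute recheck carries only its own short interval. This matches the percent-time form that item 10.2 already uses for glucose range and microdialysis. Note in the report that under 4-hourly checks each reading stands for about 4 hours and that missed episodes are not recovered. The 5-minute CGM data can serve as a sensitivity check.

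The cost is a few sentences and a little programming. Glucose values are already to be documented electronically under item 2, and no procedure or treatment rule changes. The small loss is that the figure is no longer a simple ratio of counts.
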